13.5 Analysis of Primary Endpoints

See Section 13.1

13.6 Analysis of Secondary Endpoints

The distributions of progression-free- and overall survival times will be estimated by using Kaplan-Meier analysis. Immune-related objective response rate will be estimated as described in Section 11.2. Immune-related progression-free survival (irPFS) rate is defined as time from treatment initiation to death or to immune-related progression of disease (irPD) as defined in Section 11.2. Duration of response (DoR) is defined as time from best overall response to the time of disease progression, where best overall response and disease progression are as defined in Section 11.1.

Exploratory endpoints are not specifically planned but could include biomarker expression and immune population analysis, and descriptive statistics including the mean, standard deviation, median, minimum, and maximum values, for the cohort. For baseline categorical data, the number and percentage of patients in each category will be collected. Appropriate statistical methods may be used to investigate any possible relationship of biomarker levels with response to baseline characteristics and response to study treatment.

An additional exploratory endpoint includes a comparison of the assessment of activity of mirvetuximab soravtansine in combination with pembrolizumab as described in Section 13.1 between patients with and without prior exposure to IO therapy targeting the PD-1/PD-L1 pathway. If at least 6 of the 19 patients meet the endpoint of either OR and/or PFS6 (i.e. exhibit clinical benefit), this would generate a 95% binomial coefficient of 12.6% - 56.5%, which would exclude the possibility that clinical benefit with this regimen is <10% in the IO-exposed patients.

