## 5.5.1 Tumor Response Assessments

Antitumor activity will be assessed through radiological tumor assessments conducted at baseline (screening) of starting therapy and every 2 cycles (6 weeks) thereafter. In addition, radiological tumor assessments will also be conducted whenever disease progression is suspected (eg, symptomatic deterioration) and at the time of withdrawal from the treatment (if not done in the previous 4 weeks). Complete, partial responses and progressive disease must be confirmed on repeated imaging  $\geq$  4 weeks after initial documentation, but not more than 6 weeks after initial documentation.

Assessment of response will be made using RECIST version 1.1 and as per immune-related RECIST criteria (irRECIST).

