#### Target disease

- Complete Response (CR): Complete disappearance of all target lesions with the exception of nodal disease. All target nodes must decrease to normal size (short axis <10mm). All target lesions must be assessed.
- Partial Response (PR): Greater than or equal to 30% decrease under baseline of the sum of diameters of all target measurable lesions. The short diameter is used in the sum for target nodes, while the longest diameter is used in the sum for all other target lesions. All target lesions must be assessed.
- Stable: Does not qualify for CR, PR or Progression. All target lesions must be assessed. Stable can follow PR only in the rare case that the sum increases by less than 20% from the nadir, but enough that a previously documented 30% decrease no longer holds.
- Objective Progression (PD): 20% increase in the sum of diameters of target measurable lesions above the smallest sum observed (over baseline if no decrease in the sum is observed during therapy), with a minimum absolute increase of 5mm.
- Indeterminate. Progression has not been documented, and
  - One or more target measurable lesions have not been assessed;

• Assessment methods used were inconsistent with those used at baseline;

or

• One or more target lesions cannot be measured accurately (eg, poorly visible unless due to being too small to measure);

or

• One or more target lesions were excised or irradiated and have not reappeared or increased.

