#### **Objective/Subjective**

Patients requiring discontinuation of treatment without objective evidence of disease progression should not be reported as PD on tumor assessment CRFs. This should be indicated on the end of treatment CRF as off treatment due to Global Deterioration of Health Status. Every effort should be made to document objective progression even after discontinuation of treatment.

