#### **Determination of Best Overall Response**

The best overall response is the best response recorded from the start of the treatment until disease progression/recurrence (taking as reference for progressive disease the smallest sum on study). For CR and PR, the patient's best response assignment will depend on the achievement of both measurement and confirmation criteria. CR and PR must be confirmed by 2 measurements at least 4 weeks apart. In the case of SD, follow up measurements must have met the SD criteria at least once after study entry at a minimum interval of 6 weeks.

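### Duration of response runs from best overall response to lesion-based progression: PR time before a CR is dropped, and a responder's death without documented progression is no event, with its handling unstated

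*Combined protocol and SAP*

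**What the plan says.** DoR is a secondary objective (Section 1.3), and its only definition is in Section 13.6: "Duration of response (DoR) is defined as time from best overall response to the time of disease progression". That section sends the reader to Section 11.1 for both terms.

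- **Start.** Under Determination of Best Overall Response in Section 11.1, "The best overall response is the best response recorded from the start of the treatment until disease progression/recurrence". The same paragraph adds that "CR and PR must be confirmed by 2 measurements at least 4 weeks apart".
- **End.** Progression in Section 11.1 rests on lesions. For target disease it is a "20% increase in the sum of diameters of target measurable lesions above the smallest sum observed", with a 5 mm minimum; the other routes are unequivocal non-target progression and new lesions. Under Objective/Subjective, "Patients requiring discontinuation of treatment without objective evidence of disease progression should not be reported as PD on tumor assessment CRFs".
- **Estimator.** Section 13.6 names Kaplan-Meier for PFS and OS. It names no estimator, event list or censoring rule for DoR. In the same paragraph, the irPFS definition does count death.

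**The concern.** DoR is meant to describe how long a response lasts. A clock that starts at the best category reached, rather than at the first response, leaves out time the patient spent in response whenever a PR deepens to CR. An end point limited to lesion growth has no place for a responder who dies before progression is seen. An analyst must then either improvise or censor the death, and censoring treats that patient as if the response might have continued.

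The estimate will rest on few patients: 4 responders at the ORR success threshold and 0.20 × 35 = 7 at the target rate. The handling of one or two patients can therefore be visible in the reported figure.

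**Working it through.** The documents state no DoR figure, so there is nothing to reproduce. The check reads the definitions against each other and then sizes each effect.

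**1. Start.** A patient with PR at one scan and CR at a later one has best overall response CR, so time from best overall response begins at the CR. Section 5.5.1 sets scans every 2 cycles (6 weeks) and confirmation 4 to 6 weeks after initial documentation. The loss is therefore 4 to 6 weeks if CR is first seen on the confirming scan, and more if it comes later. A patient whose first response is CR, or whose tumour shrinks further within PR, loses nothing. Section 2.3 suggests that few patients may be affected: the single-agent endometrial data mention 3 PRs with pembrolizumab and 2 with mirvetuximab soravtansine, and no CR. Five responses are too few to exclude CRs.

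**2. End, under constant hazards.** Let d be the share of responses that end in death without documented progression, and suppose those deaths are censored. The event hazard falls by the factor (1-d), so the median is multiplied by 1/(1-d):

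- d = 5%: 1/0.95 = 1.053 (+5%)
- d = 10%: 1/0.90 = 1.111 (+11%)
- d = 20%: 1/0.80 = 1.250 (+25%)

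These values of d are assumptions.

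**3. End, Kaplan-Meier median with one censored death.** All other responses end in progression at distinct times t1 < t2 < …, and the median is the first time at which S ≤ 0.5.

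- n = 4, no censoring: S = 3/4, 2/4, so the median is t2. Death at rank 1: S = 2/3 at t2 and 1/3 at t3, median t3. Death at rank 2: S = 3/4, then 3/4 × 1/2 = 0.375 at t3, median t3. Death at rank 3 or 4: still t2. Unchanged in 2 of 4 positions.
- n = 7, no censoring: S = 6/7, 5/7, 4/7, 3/7, so the median is t4. Death at rank 1: 5/6 × 4/5 × 3/4 = 0.5 at t4, unchanged. Death at rank 2, 3 or 4: S after t4 is 18/35 = 0.514, 15/28 = 0.536 or 4/7 = 0.571, so the median moves to t5. Death at rank 5, 6 or 7: unchanged. Unchanged in 4 of 7 positions.

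The curve as a whole can only stay the same or rise when an event becomes a censoring; the median may or may not move.

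**4. Both together, on invented data.** Take 7 responders with durations of 12, 18, 24, 30, 36, 42 and 48 weeks from first response. With every ending counted, the median is 30 weeks. If the 30- and 42-week patients reach CR 12 weeks after PR and are timed from CR, the durations become 12, 18, 18, 24, 30, 36 and 48, and the median is 24. If instead the endings at 18 and 24 weeks are deaths and are censored, the median is 36. With both changes it is 30 again. The cancellation comes from the inputs chosen; the example shows direction only.

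**The case against.** The strongest reply is that the protocol works to document progression before death. Section 5.5.1 states that "radiological tumor assessments will also be conducted whenever disease progression is suspected (eg, symptomatic deterioration") and also requires a scan at treatment withdrawal if none was done in the previous 4 weeks. Section 5.7 follows patients who stop for other reasons until progression, and Section 11.1 adds that "Every effort should be made to document objective progression even after discontinuation of treatment". This stands as a reason to expect few such deaths. It does not remove them: routine scans are tied to treatment cycles, no imaging interval is given for the period after treatment, and a death from toxicity or another cause need not follow progression.

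A second reply is that Section 13.6 is merely silent on deaths. That is half right. The definition ends at progression, so death is not an event, but whether the patient is censored is indeed unstated. The lengthening is therefore conditional.

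A reader might also infer that every responder loses 4 to 6 weeks because the clock could start at the confirming scan. The documents do not support this. Section 5.5.1 says "Complete, partial responses and progressive disease must be confirmed on repeated imaging" and counts the interval from initial documentation, which favours dating the response at the first scan. Section 11.1 makes assignment of the category depend on confirmation; it does not move the date. Stating the date is a useful clarification and no more.

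Finally, this is one descriptive secondary estimate with no test attached. That is correct, and it limits the weight of the point.

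**Conclusion.** The definition needs correcting. Followed literally, it drops PR time in PR-to-CR responders (one scan interval or more each, in probably few patients) and gives no event to a responder who dies without documented progression. The first effect shortens DoR; the second lengthens it, or leaves it unchanged, if those deaths are censored. The net size is unknown, because the documents give neither the frequency of PR-to-CR conversion nor d. The +5% to +25% range rests on constant hazards, censored deaths and an assumed d of 5% to 20%.

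Two stronger readings should be resisted. One is that DoR will be overstated overall: the effects oppose each other, so no net direction can be claimed. The other is that a single censored death must inflate the median by a third with 4 responders or a sixth with 7. Those figures come from n/(n-1) (4/3 and 7/6), which holds for an exponential estimate with all responses ended. The Kaplan-Meier median is unchanged in half or more of the possible positions.

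The co-primary decision rule, alpha and power are untouched.

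**What to change.** In Section 13.6, define DoR in patients with confirmed CR or PR as the time from the first documented CR or PR, whichever comes first and is later confirmed, to the first RECIST 1.1 progression under Section 11.1 or death from any cause, whichever comes first. Estimate it by Kaplan-Meier, with event-free patients censored at the last adequate tumour assessment.

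This is a wording change in one section. Scan dates follow from Section 5.5.1 and dates of death from Section 5.6, so no new data or visits are needed. The reported median may shift in either direction: up where PR time is restored, down where deaths count as events. A death long after the last scan would also credit unobserved time as response, so the plan should state how a death after missed assessments is treated.

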#### 13.7 **Reporting and Exclusions**

#### 13.7.1 Evaluation of Toxicity

All participants will be evaluable for toxicity from the time of their first treatment.

#### 13.7.2 Evaluation of the Primary Efficacy Endpoint

All participants included in the study must be assessed for response to treatment, even if there are major protocol treatment deviations or if they are ineligible. Each participant should be assigned one of the following categories: 1) complete response, 2) partial response, 3) stable disease, 4) progressive disease, 5) early death from malignant disease, 6) early death from toxicity, 7) early death because of other cause, or 9) unknown (not assessable, insufficient data). By arbitrary convention, category 9 usually designates the "unknown" status of any type of data in a clinical database.

All participants who have measurable disease present at baseline, have received at least one cycle of therapy, and have had their disease re-evaluated will be considered evaluable for response. Participants in response categories 5-9 will not be considered evaluable but will remain within the intention to treat analysis.

Patients who develop brain metastasis on study, but continue on study after definitive treatment of their cranial disease, will be considered to have had progressive disease at the point of the diagnosis of the initial brain metastasis.

All conclusions should be based on all evaluable participants. Subanalyses may then be performed on the basis of a subset of participants, excluding those for whom major protocol deviations have been identified (e.g., early death due to other reasons, early discontinuation of treatment, major protocol violations, etc.). However, these subanalyses may not serve as the basis for drawing conclusions concerning treatment efficacy, and the reasons for excluding participants from the analysis should be clearly reported. The 95% confidence intervals should also be provided.

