### **REGISTRATION PROCEDURES**

### 4.1 General Guidelines for DF/HCC Institutions

Institutions will register eligible participants in the Clinical Trials Management System (CTMS) OnCore. Registrations must occur prior to the initiation of any protocol-specific therapy or intervention. Any participant not registered to the protocol before protocol-specific therapy or intervention begins will be considered ineligible and registration will be denied.

An investigator will confirm eligibility criteria and a member of the study team will complete the protocol-specific eligibility checklist.

Following registration, participants may begin protocol-specific therapy and/or intervention. Issues that would cause treatment delays should be discussed with the Overall Principal Investigator (PI). If the subject does not receive protocol therapy following registration, the subject must be taken off-study in the CTMS (OnCore) with an appropriate date and reason entered.

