## 4.3 General Guidelines for Other Investigative Sites

Eligible participants will be entered on study centrally at the Dana-Farber Gynecologic Oncology Coordinating Center by the Project Manager. All sites should contact the Project Manager ([name]; [name]\[contact]) when a potential participant is identified to confirm enrollment availability.

Following registration, participants should begin protocol therapy within 5 days. Issues that would cause treatment delays should be discussed with the Overall PI. If the subject does not receive protocol therapy following registration, the subject must be taken off study in the CTMS (OnCore) with an appropriate date and reason entered.

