#### 11.1.2 Recording Tumor Assessments

All sites of disease must be assessed at baseline. Baseline assessments should be done as close as possible prior to study start. For an adequate baseline assessment, all required scans must be done within 28 days prior to treatment and all disease must be documented appropriately. If baseline assessment is inadequate, subsequent statuses generally should be indeterminate.

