#### 13.1 Study Design/Endpoints

#### Primary Endpoints

To assess the activity of mirvetuximab soravtasine in combination with pembrolizumab in patients with recurrent or persistent MSS and FR $\alpha$  positive endometrial cancer by evaluating the frequency of patients who survive progression-free for at least 6 months (PFS6) after initiating therapy or have objective tumor response.

Statistical considerations are developed for co-primary objectives to evaluate the objective response rate (ORR) by RECIST 1.1 and rate of progression-free survival at 6 months (PFS6), with a two-stage design that allows for early stopping for futility.

A two-stage test was constructed using the method of Sill, Rubinstein, Litwin and Yothers [36] with the goal of stopping early for futility to limit patient exposure to an inactive agent while restricting the probabilities of type I and type II errors to approximately 10% and 15%, respectively. For the co-primary endpoints, a true ORR of 5% or less and a rate of progressionfree survival at 6 months of (PFS6) 10% or less would not be of clinical interest (H0:  $\pi_{OR} \leq 5\%$ AND  $\pi_{PFS6} \le 10\%$ ), whereas an improvement to a 20% objective response rate or 30% PFS6 rate would warrant further investigation of the study treatment. In the first stage, 16 patients will be enrolled and accrual will pause. If there are at least two objective responses or two patients progression-free at 6 months among the first 16 patients, the second stage of accrual will commence where an additional 19 patients will be enrolled. If at the end of the trial there are at least 4 treated patients with an objective response or 8 patients progression-free at 6 months, the study treatment will be considered worthy of further study. Specifically, analysis of historical data (GOG129 and GOG229 series) based on similar population of patients with endometrial cancer where the levels of activity were believed to be inactive to modestly active shows that an unacceptable rate for objective response ( $\pi_{OR}$ ) is 5% and for PFS6 ( $\pi_{PFS6}$ ) is 10%, respectively. A bivariate test of the co-primary endpoints is constructed as follows:

H0:  $\pi_{OR} \leq 5\%$  AND  $\pi_{PFS6} \leq 10\%$ 

vs. H1:  $\pi_{OR} > 5\%$  OR  $\pi_{PFS6} > 10\%$ 

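### Section 13.7.2 rests all conclusions on evaluable participants, in conflict with the treated-patient counts in 13.1; once there is a responder, excluding early deaths and unknowns raises the reported ORR and its 95% CI

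*Combined protocol and SAP*

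**What the plan says.** Section 13.7.2 requires every participant to be assigned a response category, including ineligible patients and those with major deviations. Evaluable for response means measurable disease at baseline, at least one cycle received, and a re-evaluation of disease. For early deaths (categories 5 to 7, by cause) and unknowns (category 9) it says: "Participants in response categories 5-9 will not be considered evaluable but will remain within the intention to treat analysis". It then sets the basis for inference: "All conclusions should be based on all evaluable participants". It asks for 95% confidence intervals without naming their denominator.

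Section 13.1 works with counts. Accrual resumes on this condition: "If there are at least two objective responses or two patients progression-free at 6 months among the first 16 patients". At the end the regimen is worth further study with "at least 4 treated patients with an objective response or 8 patients progression-free at 6 months". Section 13.5, on the primary analysis, says only "See Section 13.1".

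**The concern.** The plan gives two instructions for the primary endpoint. Section 13.1 counts over the first 16 and over treated patients. Section 13.7.2, whose title names the primary efficacy endpoint, removes early deaths and unknowns before anything is concluded. The intention-to-treat analysis that would retain them supports no conclusion as the text stands.

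Section 13.7.2 also pulls against itself. It gives early death for other reasons as an example of an exclusion allowed only in subanalyses that cannot support efficacy conclusions. Yet category 7, early death from another cause, is already outside the set on which all conclusions rest.

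At stake are the reported ORR and its interval, which readers will set against the 5% null rate. A patient who dies early of toxicity would leave the efficacy denominator, so early toxic deaths would make the response rate look better.

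**Working it through.** **Inputs.** From 13.1 and Table 12: 16 patients in stage 1 and 35 in total; continue with at least 2 responses or at least 2 PFS6 successes; final thresholds 4 and 8; null rates 5% and 10%; targets 20% and 30%. From 13.7.2: categories 5-7 and 9 are not evaluable. The number excluded, k, is not in the documents and is an assumption throughout.

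**1. The plan's own figures, independence rows of Table 12.** The probability of stopping early is P(X≤1 | 16, 0.05) × P(Y≤1 | 16, 0.10) = 0.8108 × 0.5147 = 0.417, as printed. Exact enumeration of both stages gives alpha 0.0977 (printed 0.098), and power 0.8885 for response and 0.8728 for PFS6 (printed 0.889 and 0.873). These figures rest on counts over all 16 and all 35 patients.

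**2. Effect on the decision.** Nobody in categories 5-9 is a responder, so the response count r is the same over treated or evaluable patients. With all treated patients counted, as 13.1 states, thresholds, alpha and power stay as in step 1.

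**3. Effect on the reported ORR.** The all-treated estimate is r/35 and the evaluable-only estimate is r/(35-k). For r≥1 the ratio is 35/(35-k):

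- k=1: 35/34 = 1.03
- k=2: 35/33 = 1.06
- k=5: 35/30 = 1.17

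With r=0 both estimates are zero.

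Exact (Clopper-Pearson) 95% intervals at the threshold of 4 responses:

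| Denominator | ORR | 95% CI |
|---|---|---|
| 35 (all treated) | 11.4% | 3.2-26.7% |
| 34 (k=1) | 11.8% | 3.3-27.5% |
| 30 (k=5) | 13.3% | 3.8-30.7% |

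The lower limit passes 5% only at k=13 (4/23 gives 4.95%, 4/22 gives 5.2%). At 5 responses it is 4.8% on 35, 4.95% on 34 and 5.1% on 33.

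**4. PFS6, only if the rule is extended to it.** Section 1.2 requires the patient to be alive and progression-free, so a death before 6 months is a failure. Excluding such deaths removes failures only: 8/35 = 22.9% (10.4-40.1%) becomes, with five excluded, 8/30 = 26.7% (12.3-45.9%). Unknowns have no fixed direction. Section 11.1.2 says "If baseline assessment is inadequate, subsequent statuses generally should be indeterminate", and a patient with such a baseline may in fact be progression-free at 6 months.

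**5. The IO-exposed group in 13.6.** The plan's example, 6 of 19, gives 12.6-56.5% and excludes 10%. Five of 19 does not (lower limit 9.1%). If two patients without benefit were dropped as non-evaluable, 5/17 would (10.3%). The denominator therefore needs stating there too.

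**The case against.** The strongest reply is that 13.1 governs. Its rule is a count, 13.5 points to it, and excluding non-responders cannot change a count of responders. That stands: what is left is the denominator of an estimate. The plan also never judges activity by a 95% limit against 5%. At 4 responses no realistic k moves the limit past 5%, and at 5 responses 13.1 has already declared activity. That stands as well. Nor does the retained intention-to-treat analysis settle the matter, since conclusions are assigned to the other set.

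Three stronger readings might be inferred, and the documents support none of them.

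- *Every exclusion biases ORR upward.* With no responders the rate stays at zero. A patient enrolled without measurable disease, against 3.1.2, would also be non-evaluable and might still be recorded as a responder. The claim holds for categories 5-9 with at least one responder.
- *The type I error is inflated.* That would require non-evaluable patients to be replaced until 16 and 35 evaluable ones are reached. Under independence alpha would then run from 0.116 to 0.204 for an assumed 5% to 20% non-evaluable. No section provides for replacement.
- *The PFS6 decision could be reversed by losing a progression-free patient of unknown status.* This carries a definition written for response over to PFS6. Under the all-treated rule proposed below, a patient whose 6-month status is unknown would not count as a success either.

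It is also fair to say that 13.1 uses both enrolled and treated, so choosing treated patients as the denominator is a decision and should be stated as one.

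**Conclusion.** The wording is wrong as it stands and should be corrected. Section 13.7.2 conflicts with 13.1 and leaves its own intention-to-treat analysis without a purpose. If it is followed, with at least one responder and at least one patient in categories 5-9, the reported ORR and both limits of its interval are too high. The relative rise is 3% to 17% for k from 1 to 5; that range is an assumption, because the documents give no expected number of early deaths or unknowns. A parallel rise in PFS6 from excluded early deaths depends on extending the rule to PFS6 and on those deaths falling before 6 months. Alpha (0.098 under independence), power and the go/no-go thresholds are untouched when all treated patients are counted. The effect is modest and falls on what is reported.

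**What to change.** Replace the sentence that bases all conclusions on evaluable participants with:

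> The reported ORR and PFS6, their 95% CIs, and the decisions in Section 13.1 are based on all participants who received at least one dose of study treatment. Categories 5-9 count as non-responders. Deaths before 6 months count as PFS6 failures. Participants with unknown 6-month status stay in the denominator and are not counted as successes; their number is reported. The analysis of evaluable participants is a sensitivity analysis.

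Add that registered participants who never receive treatment, a case foreseen in Sections 4.1 and 4.3, are reported separately and are outside this denominator. Use the same denominator for the IO-exposed group in 13.6.

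**Cost.** A wording amendment with IRB approval, and slightly less favourable reported rates. PFS6 may be understated when status is unknown: 8 known successes and 2 unknowns give 8/35 = 22.9%, against 10/35 = 28.6% had both been progression-free. Reporting the number of unknowns lets the reader see that range. Never-treated registrations could leave the denominator below 35. Sample size, thresholds and data collection do not change.
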